**Table 5-1. Disallowed and Concomitant Medications to Be Used with Caution**

Medication Class	Prohibited Medications	Medications to Be Used with Caution
Anticonvulsants a		Carbamazepine, Oxcarbazepine, Phenobarbital, Phenytoin
Antifungals b		Itraconazole, Ketoconazole
Antimycobacterials a	Rifapentine, Rifabutin, Rifampin	
Herbal/Natural Supplements a	St. John's Wort, Echinacea, Milk thistle (i.e., silymarin), Chinese herb sho-saiko-to (or Xiao-Shai-Hu-Tang)	

a May result in a decrease in the concentration of TAF

b May result in an increase in the concentrations of TAF

Should subjects have a need to initiate treatment with any excluded concomitant medication, including herbal/natural products/therapies, and over the counter medications, the Gilead Sciences Medical Monitor must be consulted prior to initiation of the new medication. In instances where an excluded medication is initiated prior to discussion with the Sponsor, the investigator must notify Gilead Sciences as soon as he/she is aware of the use of the excluded medication.

### **5.5. Accountability for Tenofovir Alafenamide (TAF)**

The investigator or designee (i.e., pharmacist) is responsible for ensuring adequate accountability of all used and unused IMP. This includes acknowledgement of receipt of each shipment of IMP (quantity and condition). All used and unused IMP dispensed to subjects must be returned to the site.

Investigational product accountability records will be provided to the study site to:

- Record the date received and quantity of IMP kits and/or bottles
- Record the date, subject number, subject initials, the IMP kit and/or bottles number dispensed
- Record the date, quantity of used and unused IMP kit and/or bottles returned, along with the initials of the person recording the information.

#### **5.5.1. Investigational Medicinal Product Return or Disposal**

At the start of the study, the study monitor will evaluate the study center's study drug disposal procedures and provide appropriate instruction for return or destruction of unused study drug supplies. If the site has an appropriate Standard Operating Procedure (SOP) for drug destruction, the site may destroy used and unused study drug supplies performed in accordance with the site's (hospital/pharmacy) SOP. If the site does not have acceptable procedures in place for drug destruction, arrangements will be made between the site and Gilead Sciences (or Gilead Sciences' representative) for return of unused study drug supplies. A copy of the site's SOP will be obtained for central files. Where possible, study drug will be destroyed at the site. Upon study completion, a copy of the Investigational Drug Accountability records must be filed at the site. Another copy will be returned to Gilead Sciences. If drug is destroyed on site, the investigator must maintain accurate records for all study drug kits and/or bottles destroyed. Records must show the identification and quantity of each unit destroyed, the method of destruction, and person who disposed of the drug. All study drug records must be maintained at the site and copies must be submitted to Gilead Sciences at the end of the study.

## 6. STUDY PROCEDURES

The study procedures to be conducted for each subject enrolled in the study are presented in tabular form in [Appendix 2](#) and described in the text that follows.

The investigator must document any deviation from protocol procedures and notify the sponsor.

### 6.1. Subject Enrollment and Treatment Assignment

It is the responsibility of the investigator to ensure that subjects are eligible to participate in the study prior to enrollment. Once consent has been obtained, all screening tests and procedures have been completed, and study eligibility has been confirmed, subjects will be randomized within 45 days using an IVRS/IWRS. Subjects will receive study drugs within their assigned treatment group as described in Section 3.2. Candidates who fail to meet eligibility criteria by screening evaluations may be re-screened once after the initial screen if there is a reasonable expectation that the candidate will be eligible after repeat screening.

Retesting of an exclusionary laboratory value during the Screening period is permitted only if in the Principal Investigator's opinion, the retest value will be within accepted parameters; if the initial value was deemed to be inaccurate, inconsistent with the subject's previous result(s); in error (e.g. mishandled sample); or due to an extenuating circumstance.

### 6.2. Pretreatment Assessments

**Prior** to the conduct of any screening procedures, each candidate must sign an Informed Consent Form. Consent is to be obtained in accordance with regulatory and local Ethics Committee requirements.

#### 6.2.1. Screening Visit (Day -45 to Day 1 of Treatment)

Subjects will be screened within 45 days before randomization to determine eligibility for participation in the study. The following will be performed and documented at screening:

- [REDACTED]
- [REDACTED]
- [REDACTED]

- Obtain medical history, including Hepatitis B history and treatment history
- Review of inclusion/exclusion criteria

- Review of AEs and concomitant medications
- Perform complete physical examination including, vital signs (blood pressure, pulse, respiration rate and temperature), body weight, and height
- Perform DXA scan of spine and hip. DXA scan will be performed at any time during the Screening period and should be completed at least 14 days prior to the first dose of the study drug, in order to ensure an acceptable pre-dose DXA scan
- Obtain blood samples for laboratory assessments as follows:
  - Safety laboratory tests (serum chemistry, hematology, and coagulation)
  - Quantification of plasma HBV DNA levels
  - Qualitative HBsAg and HBeAg (HBsAb and HBeAb reflex testing will be performed as needed)
  - Other viral serology (HCV, HIV and HDV)
  - eGFRCKD-EPI
  - Serum  $\beta$ -hCG pregnancy test (for all female subjects of child-bearing potential)
  - Alpha-fetoprotein (AFP). Subjects with an AFP >50 ng/mL or other findings concerning HCC must have an appropriate evaluation (e.g., CT scan) to rule out HCC prior to being able to enter into the study
- Obtain urine sample for urinalysis, and urine drug screen
- Record any serious adverse events (SAE) and all adverse events (AE) related to protocol mandated procedures occurring after signing of the consent form.

Subjects meeting all of the inclusion criteria and none of the exclusion criteria will return to the clinic within 45 days after screening for randomization into the study.

From the time of obtaining informed consent through the first administration of investigational medicinal product, record all serious adverse events (SAEs), as well as any adverse events related to protocol-mandated procedures on the adverse events case report form (CRF/eCRF). All other untoward medical occurrences observed during the screening period, including exacerbation or changes in medical history are to be captured on the medical history CRF/eCRF. See Section 7 Adverse Events and Toxicity Management for additional details.

### 6.2.2. Baseline Assessments (Day 1)

All baseline tests and procedures must be completed prior to the receipt of the first dose of study drug. Subjects screened within 45 days before Baseline will be eligible to participate in the study. Initiation of treatment with study drug should take place on the day of the Baseline visit. The following will be performed at the Baseline visit:

- Review of medical history, HBV history and HBV treatment history on any changes since screening visit
- Provide Health Related Quality of Life surveys (HRQoL): SF-36, CLDQ, WPAI to be completed by subjects at visit
- Perform complete physical examination including, vital signs (blood pressure, pulse, respiration rate and temperature), and body weight
- Review of inclusion/exclusion criteria
- Review of AEs and concomitant medication
- Complete the “Fracture Risk Assessment” (FRAX®) eCRF
- Cr EDTA Renal Scan
- Obtain blood samples for laboratory assessments as follows:
  - Safety laboratory tests (serum chemistry, hematology, and coagulation)
  - Quantification of plasma HBV DNA levels
  - Qualitative HBsAg and HBeAg (HBsAb and HBeAb reflex testing will be performed as needed)
  - eGFRCKD-EPI
  - Blood sample for Vitamin D assessment
  - Blood sample for Fibrotest®
  - Blood sample for PBMC
  - Blood sample for PK
  -  
  - HBV resistance surveillance

- Randomization
- Fasting blood sample for bone, renal biomarkers and metabolic assessment (glucose and lipid panel [total cholesterol, HDL, direct LDL, and triglycerides]) – no food or drinks, except water, at least 8 hours prior to blood collection
- Fasting urine sample for renal biomarkers
- [REDACTED]
- Pregnancy test (for females of child-bearing potential; in case of a positive urine test, a serum pregnancy test will be done)

### 6.3. Treatment Assessments

#### 6.3.1. Study Week Assessments (Weeks 4-48)

The following evaluations will be performed at Weeks 4-48 unless specified;

- Provide Health Related Quality of Life surveys (HRQoL): SF-36, CLDQ, WPAI to be completed by subjects at visit (**Weeks 24, and 48 only**)
- Perform complete physical examination including, vital signs (blood pressure, pulse, respiration rate and temperature), and body weight (**Weeks 12, 24, and 48 only**)
- Perform symptom-driven physical examination including vital signs, and body weight (**Weeks 4, 8, 20, and 36 only**)
- Review of AEs and concomitant medications
- Cr EDTA Renal Scan (**Week 48 only**)
- Perform DXA scan of spine and hip (**Weeks 24 and 48 only**)
- Perform study drug accountability
- Dispense study drugs

- Obtain blood samples for laboratory assessments as follows:
  - Safety laboratory tests (serum chemistry, hematology, and coagulation)
  - Quantification of plasma HBV DNA levels
  - Qualitative HBsAg and HBeAg (HBsAb and HBeAb reflex testing will be performed as needed) (**Weeks 24 and 48 only**)
  - eGFRCKD-EPI
  - Blood sample for Fibrotest® (**Weeks 24 and 48 only**)
  - Blood sample for Vitamin D assessment (**Weeks 24 and 48 only**)
  - Blood sample for AFP (**Weeks 24 and 48 only**)
  - Blood sample for PK
  - 
  - Blood sample for PBMC (**Weeks 24 and 48 only**)
  - 
  - HBV resistance surveillance
- Dose in clinic and collect single blood sample for plasma PK between 15 minutes to 4 hours post-dose. Subjects who elect to dose in the evening the previous day are not required to have in-clinic dosing, the plasma PK samples from these subjects can be collected anytime (not timed) (**Weeks 8 and 24 only**)
- Urine pregnancy test (for all female subjects of child-bearing potential)
- Urinalysis (**Weeks 4, 12, 24, and 48 only**)
- Fasting blood sample for bone and renal biomarkers – no food or drinks, except water, at least 8 hours prior to blood collection (**Weeks 4, 12, 24, and 48 only**)
- Fasting urine sample for renal biomarkers (**Weeks 4, 12, 24, and 48 only**)
- Fasting blood sample for metabolic assessment (glucose and lipid panel [total cholesterol, HDL, direct LDL, and triglycerides]) – no food or drinks, except water, at least 8 hours prior to blood collection (**Weeks 24 and 48 only**)

[REDACTED]

[REDACTED]

[REDACTED]

[REDACTED]

[REDACTED]

[REDACTED]

[REDACTED]

[REDACTED]

[REDACTED]

[REDACTED]

[REDACTED]

[REDACTED]

[REDACTED]

[REDACTED]

**CCI** [REDACTED]

[REDACTED]

[REDACTED]

[REDACTED]

[REDACTED]

[REDACTED]

[REDACTED]

[REDACTED]

[REDACTED]

[REDACTED]

[REDACTED]

[REDACTED]

- Review of AEs and concomitant medications
- Perform DXA scan of spine and hip
- Perform study drug accountability
- Obtain blood samples for laboratory assessments as follows:
  - Safety laboratory tests (serum chemistry, hematology, and coagulation)
  - Quantification of plasma HBV DNA levels
  - Qualitative HBsAg and HBeAg (HBsAb and HBeAb reflex testing will be performed as needed)
  - eGFRCKD-EPI
  - Blood sample for Fibrotest®
  - Blood sample for Vitamin D assessment
  - Blood sample for AFP
  - 
  - HBV resistance surveillance
- Urine pregnancy test (for all female subjects of child-bearing potential)
- Urinalysis
- Fasting blood sample for bone and renal biomarkers – no food or drinks, except water, at least 8 hours prior to blood collection
- Fasting urine sample for renal biomarkers
- Fasting blood sample for metabolic assessment (glucose and lipid panel [total cholesterol, HDL, direct LDL, and triglycerides]) – no food or drinks, except water, at least 8 hours prior to blood collection

## 6.4. Post-Treatment Assessments

### 6.4.1. All Other Subjects Who Discontinue TAF

Subjects who have received at least one dose of TAF and discontinue treatment prematurely CC will be followed every 4 weeks for 24 weeks off treatment in accordance with TFFU schedule of assessments or until initiation of alternative CHB therapy, whichever comes first.

#### 6.4.1.1. Treatment Free Follow-Up (TFFU) Visit Assessments ( $\pm$ 7 Days)

The following evaluations will be performed at follow up visits for subjects when they discontinue TAF unless otherwise specified. For more details, refer to [Appendix 2](#).

- Review of AEs and concomitant medications
- Symptom-directed physical examination
- Collect vital signs and body weight
- Urine pregnancy test (for all female subjects of child-bearing potential)
- Urinalysis
- Obtain blood samples for laboratory assessments as follows:
  - Serum chemistry, hematology and coagulation tests
  - Quantification of plasma HBV DNA levels
  - Qualitative HBsAg and HBeAg (HBsAb and HBeAb reflex testing will be performed as needed)
  - eGFRCKD-EPI
  - CC
  - HBV resistance surveillance

## 6.5. Assessments for Premature Discontinuation from Study

If a subject discontinues study dosing (for example, as a result of an AE), every attempt should be made to keep the subject in the study and continue to perform the required study-related follow-up and procedures (see Section 6.6, Criteria for Discontinuation of Study Treatment). If this is not possible or acceptable to the subject or investigator, the subject may be withdrawn from the study.

## 6.6. Criteria for Discontinuation of Study Treatment

Study medication may be discontinued in the following instances:

- Intercurrent illness that would, in the judgment of the investigator, affect assessments of clinical status to a significant degree. Following resolution of intercurrent illness, the subject may resume study dosing at the discretion of the investigator.
- Unacceptable toxicity, as defined in the toxicity management section of the protocol, or toxicity that, in the judgment of the investigator, compromises the ability to continue study-specific procedures or is considered to not be in the subject's best interest
- Subjects with confirmed  $eGFR_{CKD-EPI}$  of  $< 15 \text{ mL/min/1.73m}^2$  at any time during the study will have their study drug permanently discontinued
- Lack of efficacy (virologic failure)
- HBsAg loss with seroconversion to anti-HBs. These subjects should discontinue study drug within 3-6 months following confirmation of seroconversion to anti-HBs. Subjects with HBsAg loss with confirmed seroconversion before Week 48 are not permitted to discontinue study drug prior to the Week 48 visit
- Discontinuation of study drug for subjects experiencing HBsAg-loss with confirmed seroconversion to anti-HBs, who have known bridging fibrosis or cirrhosis, should be considered on a case by case basis
- Subject request to discontinue for any reason
- Subject noncompliance
- Pregnancy during the study; refer to [Appendix 6](#)
- Discontinuation of the study at the request of Gilead, a regulatory agency or an institutional review board or independent ethics committee (IRB/IEC)

CCI

CCI

CCI

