### 1.3. Rationale and Risk/Benefit Assessment for this Study

While the number of liver transplants for CHB consequences is low in the United States (~350/year), in countries with high prevalence of CHB, HBV remains the most important cause of liver transplantation {Lee 2015}. Without prophylaxis, patients with CHB receiving a liver transplant have near universal re-infection of the graft {Samuel 1993}. Current practice is to treat prior and post-transplant patients with oral nucleos(t)ide polymerase inhibitors and Hepatitis B Immunoglobulin (HBIG) to prevent infection of the new liver. Study 203-0107 demonstrated in a small group of post-liver transplant patients that treatment with TDF/FTC alone was equivalent to TDF/FTC + HBIG after 72 weeks of follow-up {Teperman 2013}. With these interventions, infection of the graft has been reduced to < 10% {Katz 2010}. While practice patterns for continuation of HBIG can vary by center, all patients must remain on lifelong nucleos(t)ide analog treatment.

After receiving a liver transplant, the majority of patients develop some degree of chronic kidney disease, with over 18% having a GFR < 30 ml/min within 5 years of transplant mainly as a result of the use of calcineurin inhibitors (CNI) {Lucey 2013, Ojo 2003}. CNIs are a mainstay of immunosuppression immediately after transplantation and can lead to acute or chronic kidney injury through hemodynamic changes or direct nephrotoxic effects. While some centers reduce or eliminate CNIs from immunosuppressive regimens over time, many continue patients lifelong on CNIs. Even in those patients who stop CNIs, the renal effects are often not reversible. This persistent renal dysfunction, therefore, can complicate antiviral treatment with medications such as TDF.

For these patients who have received a liver transplant and have renal insufficiency, TAF may provide an alternative to currently used treatments by achieving viral suppression while resulting in improved safety of bone and renal parameters compared to TDF-based regimens.

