### 3.4. Duration of Treatment

The duration of the study treatment is 48 weeks with an initial screening period of 45 days. Subsequent to Screening, subjects will be randomized to receive TAF or TDF alone or in combination with approved antivirals per local practice.

At Week 48, per Principal Investigator (PI) discretion, subjects will be eligible to receive TAF 25 mg daily and CCI

they will be followed for 24 weeks after the discontinuation of TAF (i.e., Treatment Free Follow-Up, TFFU) or until an alternative CHB treatment is started, whichever occurs first.

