#### **Elevated Liver Enzymes, Normal or Stable relative to baseline Liver Function Tests**

If ALT levels are elevated (i.e.,  $> 2 \times$  baseline and  $> 10 \times$  ULN) with normal or stable total bilirubin and INR relative to baseline, the subject may remain on study medication and should be monitored weekly as long as ALT levels return to normal or baseline level.

During monitoring, if the ALT values remain persistently elevated, the investigator should discuss with the Gilead Medical Monitor whether the study drug should be discontinued.

For subjects with bridging fibrosis or cirrhosis, study drug discontinuation with treatment-free follow-up is to be avoided due to the potential risk of exacerbation of hepatitis in the setting of low hepatic reserve which could lead to decompensation. Subjects with bridging fibrosis or cirrhosis should be placed on commercially available HBV therapy following study drug discontinuation.

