#### **7.5.6.2. Management of Exacerbation of Hepatitis in Subjects Who Have Discontinued Study Medication**

If laboratory results indicate (1) an ALT elevation  $> 2 \times$  baseline and  $> 10 \times$  ULN alone OR associated with (2) abnormal laboratory parameters suggestive of worsening hepatic function (total bilirubin  $2 \times$  baseline, INR 0.5 above baseline, provided both are  $> ULN$ ) and the subject is on no post-study therapy for HBV, the following is recommended:

- Schedule the subject to return to the clinic as soon as possible (ideally no later than 3 days after the initial laboratory values were drawn). During the visit, perform a clinical assessment of the subject.
- Check the following laboratory parameters: serum ALT and AST, total bilirubin, INR, and albumin.
- If the ALT elevation is confirmed, the central clinical laboratory will conduct reflex testing for plasma HBV DNA, serology for HBV (HBsAg and HBsAb), HDV, HAV IgM, HCV and HEV. If Plasma HBV DNA is increasing, the investigator should consider immediate initiation of approved therapy.
- The subject should be followed until laboratory parameters (ALT, total bilirubin, INR) return to normal or baseline up to a maximum of 6 months after the initial occurrence of the event.

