3.7.2. Analysis Visit Windows

Subject visits might not occur on protocol-specified days. Therefore, for the purpose of analysis, observations will be assigned to analysis windows.

The following windows (Table 3-1 to Table 3-5) apply to baseline and on-treatment assessments only. For summaries and analysis, assessments will first be categorized into baseline and on-treatment assessments occurring during the randomized CCI phase, before applying analysis windows.

For subjects who prematurely discontinued the randomized study drug CCI, laboratory assessments up to and including the last dose date of the randomized study drug + 3 days, and DXA assessments up to and including the last dose date of the randomized study drug + 14 days, will be considered as baseline or on-treatment during the randomized phase.

CCI

For subjects who have not discontinued the randomized study drug permanently, data collected up to database finalization date will be considered as baseline or on-treatment of the randomized phase.

CCI

CCI
 CCI

For subjects who discontinue study drug early due to HBsAg loss with confirmed seroconversion, all efficacy data including data collected after the last dose date of the study drug will be reassigned analysis visits using the on-treatment assessment windows (Table 3-1 and Table 3-3).

The analysis windows for HBV DNA, hematology, serum chemistry and liver function tests, eGFR (by CG and CKD-EPI), renal biomarkers urine albumin to creatinine ratio (UACR), urine protein to creatinine ratio (UPCR), renal tubular maximum reabsorption rate of phosphate to the glomerular filtration rate (TmP/GFR), urine fractional excretion of filtered phosphate (FEPO₄), fractional excretion of uric acid (FEUA), non-fasting glucose, weight, and vital sign assessments are provided in Table 3-1.

Table 3-1. Analysis Visit Windows for HBV DNA, Hematology, Serum Chemistry and Liver Function Tests, eGFR (by CG and CKD-EPI), UACR, UPCR, TmP/GFR, FEPO₄, FEUA, Non-fasting Glucose, Weight, and Vital Sign Assessments

Nominal Visit	Nominal Study Day	Lower Limit	Upper Limit
Baseline			1
Week 4	28	2	41
Week 8	56	42	69
Week 12	84	70	111
Week 20	140	112	153
Week 24	168	154	209
Week 36	252	210	293
Week 48	336	294	377 (419 ^b)

[figure not shown]
CCI
 CCI

^b Applies to UACR, UPCR, TmP/GFR, FEPO₄ and FEUA only.

The analysis window for Fasting Glucose, Serum Cystatin C and eGFR by CKD-EPI Cystatin C is in Table 3-2.

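### Section 6.6 says HBsAg seroconverters should stop study drug, while Section 1.3 says these transplant recipients need lifelong nucleos(t)ide therapy: a minor patient-safety correction

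*Protocol*

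**What the plan says.** **The stop.** The list in Protocol Section 6.6 opens permissively, naming circumstances in which study medication may be stopped. The seroconversion bullet is firmer: "These subjects should discontinue study drug within 3-6 months following confirmation of seroconversion to anti-HBs". Two limits follow. Nobody may stop for this reason before the Week 48 visit, and stopping in seroconverters "who have known bridging fibrosis or cirrhosis, should be considered on a case by case basis".

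**The rationale.** Section 1.3 notes that centres differ on continuing hepatitis B immunoglobulin after transplantation, but says that "all patients must remain on lifelong nucleos(t)ide analog treatment".

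**After a stop.** Section 3.4 says of subjects stopping TAF that "they will be followed for 24 weeks after the discontinuation of TAF". Section 6.4.1 says that they "will be followed every 4 weeks for 24 weeks off treatment in accordance with TFFU schedule of assessments". In both places the follow-up ends sooner if another chronic hepatitis B treatment is started. Section 6.4.1.1 lists HBV DNA, HBsAg and HBeAg, and serum chemistry among the tests at these visits.

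**Replacement therapy.** Under ALT-flare management, Section 7.5.6.1 says: "Subjects with bridging fibrosis or cirrhosis should be placed on commercially available HBV therapy following study drug discontinuation". For an exacerbation in a subject already off study drug and on no other HBV therapy, Section 7.5.6.2 says, once the ALT rise is confirmed: "If Plasma HBV DNA is increasing, the investigator should consider immediate initiation of approved therapy".

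**The SAP.** Section 3.7.2 has a visit-window rule that begins "For subjects who discontinue study drug early due to HBsAg loss with confirmed seroconversion".

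**The concern.** Every subject is a liver transplant recipient with chronic HBV before the transplant (Section 4.2), so Sections 6.6 and 1.3 speak about the same people. One says that a seroconverter should come off study drug; the other says that such a patient must stay on this class of drug for life. A site following Section 6.6 to the letter could withdraw antiviral therapy from a graft recipient and find no visible instruction to replace it.

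The group left exposed is seroconverters without known bridging fibrosis or cirrhosis. The protocol recognises the danger of an untreated interval elsewhere: Section 7.5.6.1 advises against treatment-free follow-up in subjects with bridging fibrosis or cirrhosis because of the risk of exacerbation. It gives no corresponding visible caution for transplant status, which all subjects share. What is at stake is the safety of a few subjects at most, not the trial's comparison.

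**Working it through.** There is no planned figure to reproduce, and no calculation decides the point. The check is whether the provisions can be read together.

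1. **Is the stop an instruction?** Partly. The list heading is permissive, but the seroconversion bullet says what should happen and gives a time frame. Individual judgement is reserved for bridging fibrosis or cirrhosis, so stopping reads as the default for other seroconverters.

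2. **Does Section 1.3 make an exception for seroconverters?** No. It covers all patients in the post-transplant setting.

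3. **Does stopping study drug mean stopping nucleos(t)ide therapy?** Not by definition, but in the TAF arm it can. Section 5.4 has the oral antiviral regimen taken at Screening end at Day 1, so TAF may be the only HBV antiviral. The visible follow-up after TAF is also named treatment-free.

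4. **Is replacement therapy required?**

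| Provision | Who it covers | Strength |
|---|---|---|
| Sections 3.4 and 6.4.1 | subjects stopping TAF | alternative therapy allowed; follow-up then ends |
| Section 7.5.6.1 | bridging fibrosis or cirrhosis, under ALT-flare management | should be placed on therapy |
| Section 7.5.6.2 | off study drug, confirmed ALT rise, HBV DNA rising | to be considered |

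   None requires replacement therapy at the time of a seroconversion stop. Section 7.5.6.2 is rescue after an event, not prevention.

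5. **Can the rule come into play?** Yes. It operates from Week 48 on, and visible notes to Protocol Appendix 2 schedule HBsAg testing at Weeks 72 to 192. The SAP, signed in June 2021, still has a rule for subjects who stop for this reason.

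6. **How often?** The documents cannot say. The seroconversion analysis set requires HBsAg positivity at baseline (SAP Section 3.1.5). Entry does not require it (Protocol Section 4.2), and the number positive is not given. The only seroconversion count in the documents is from the two Phase 3 studies: 3 at Week 48 among 285 + 140 + 581 + 292 = 1298 subjects, or 3/1298 = 0.23%. Those subjects were viremic and had not been selected as transplant recipients. The count supports calling the event rare, but not a rate for this trial.

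7. **Are the endpoints affected?** No. The stop is barred before the Week 48 visit, so the Week 24 and Week 48 assessments precede it.

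**The case against.** The strongest reply is redaction. The rule can operate only from Week 48, which is the period largely blacked out: the post-Week-48 sentences in Sections 3.4 and 5.3, Sections 6.7 and 6.8, Appendix 3, and part of the sentence in Section 6.4.1 defining who enters treatment-free follow-up. A reader might infer that the plan has no replacement rule. The documents do not support that; the hidden text may contain one. What stands is the visible instruction to stop, which no redaction removes.

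Second, Section 1.3 is background describing practice, and stopping a trial-supplied drug is not the same as stopping HBV treatment. A careful site could satisfy both sections by moving the subject to local therapy. That is true, and a reader who infers that the protocol orders 24 untreated weeks goes too far: 24 weeks is a monitoring period that ends when other therapy starts. But compliance then depends on the site combining two sections that point in different directions.

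Third, the safeguards are real. Visits every 4 weeks with HBV DNA, serology and liver chemistry, plus early recall for an ALT flare, should detect reactivation. They detect it; they do not prevent it.

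Fourth, other reasons in Section 6.6, such as virologic failure or low eGFR, also carry no replacement instruction there. That is so, but those stops answer a treatment problem. This one follows a favourable outcome and can simply be left out.

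Two stronger readings on size also fail.

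- Section 1.3 describes near-universal graft re-infection without prophylaxis. A reader might apply that to seroconverters, but the documents give no risk for patients with confirmed anti-HBs.
- A reader might borrow the Phase 3 rate. The chance of at least one event by Week 48 would be 1 − (1 − 0.00231)^5 = 1.2% if 5 of 50 subjects were HBsAg-positive, and 1 − (1 − 0.00231)^50 = 10.9% if all 50 were. The spread comes entirely from an assumed count, the rate is from a different population, and later treatment is not counted. Neither figure is an estimate for this trial.

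**Conclusion.** The point holds as a visible inconsistency. Under a permissive heading, Section 6.6 says that HBsAg seroconverters without known bridging fibrosis or cirrhosis should stop study drug. Section 1.3 says that no patient in this population should be without lifelong nucleos(t)ide therapy. The visible text permits replacement and monitors closely, but does not require replacement for this stop.

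The correction is minor. The event is expected to be rare, its rate cannot be derived, and no size of harm can be claimed. No planned statistical figure changes. The conclusion rests on the visible text only; if a redacted section already requires a switch, what remains is to align the wording of Section 6.6 with it.

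**What to change.** **Preferred:** delete the seroconversion stop from Section 6.6 for this post-transplant study, together with the linked sentence on bridging fibrosis or cirrhosis. The SAP Section 3.7.2 rule can stay for any subject who stops anyway.

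**Alternative:** state in Section 6.6 that study drug may be stopped for HBsAg seroconversion only with an immediate switch to an approved HBV nucleos(t)ide analogue, dosed for renal function. The dosing clause matters: entry is allowed down to an eGFR of 15 mL/min/1.73 m², and Section 7.5.5.1 already requires less frequent TDF dosing when eGFR falls below 50 and again below 30.

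**Cost:** a short edit to Section 6.6, with no added visits, samples or subjects and no change to the Week 24 or Week 48 analyses. The small downside is that seroconverters stay on antiviral therapy, which is what Section 1.3 already calls for.
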